2.1.1. Phase definitions

The phases in the study will be constructed as follows for all groups:

Table 1: Phase Definitions of Cohort 1, 2 and 3

Phase	Phase number	Period	Period number	Interval	
				From	To
Screening	1			00:00 of the date of signing the informed consent form ^a	One minute prior to Dose 1 on Day 1
Regimen	2	Post-Dose 1	1	Date and time of Dose 1 (Day 1)	Minimum of: 
 a) 23:59 at the date of database cut-off b) Maximum (28 days after first vaccination at 23:59, scheduled visit 4 weeks after first vaccination at 23:59) c) 23:59 at the date of last contact (for early discontinuation of the study)
Follow-Up 1	3			1 minute after end of Post-Dose 1 period	Minimum of: 
 a) 23:59 at the date of database cut-off b) One minute prior to date and time of the next vaccination c) 23:59 at the date of last contact (for completed and early discontinuation of the study)

Table 1: Phase Definitions of Cohort 1, 2 and 3

Phase	Phase number	Period	Period number	Interval	
				From	To
Regimen	2	Post-Dose 2	2	Date and time of Dose 2 (Day 57)	Minimum of: a) 23:59 at the date of database cut-off b) Maximum (28 days after second vaccination at 23.59, scheduled visit 4 weeks after second vaccination at 23:59) c) 23:59 at the date of last contact (for early discontinuation of the study)
Follow-Up 2	4			1 minute after end of Post-Dose 2 period	Minimum of: a) 23:59 at the date of database cut-off b) One minute prior to date and time of the next vaccination c) 23:59 at the date of last contact (for completed and early discontinuation of the study)
Regimen	2	Post-Boost (Month 12)	3	Date and time of Month 12 Boost	Minimum of: a) 23:59 at the date of database cut-off b) Maximum (28 days after the Month 12 boost vaccination at 23.59, scheduled visit 4 weeks after the Month 12 boost vaccination at 23:59) c) 23:59 at the date of last contact (for early discontinuation of the study)
Follow-Up Boost (Month 12)	5			1 minute after end of Post-Boost (Month 12) period	Minimum of: a) 23:59 at the date of database cut-off b) One minute prior to date and time of the next vaccination c) 23:59 at the date of last contact (for completed and early discontinuation of the study)
Regimen	2	Post-Boost (Month 24)	4	Date and time of Month 24 Boost	Minimum of: a) 23:59 at the date of database cut-off b) Maximum (28 days after the Month 24 boost vaccination at 23.59, scheduled visit 4 weeks after the Month 24 boost vaccination at 23:59) c) 23:59 at the date of last contact (for completed and early discontinuation of the study)

Table 1: Phase Definitions of Cohort 1, 2 and 3

Phase	Phase number	Period	Period number	Interval	
				From	To
Follow-Up Boost (Month 24)	6			1 minute after end of Post-Boost (Month 24) period	Minimum of: a) 23:59 at the date of database cut-off b) 23:59 at the date of last contact (for completed and early discontinuation of the study)

^a in case an earlier date is available (eg. for lab or vital signs), then use the very first date to include all data

In case the one-dose regimen is selected (Groups 11 through 16 from Cohort 2) after the evaluation of Cohort 2, then the post dose 2 and follow up 2 will not be applicable.

2.1.2. Immunogenicity Visit Windows

For immunogenicity summaries and tabulations per time point, assessments will be allocated to an analysis visit based on the planned visit as captured in the CRF. Visits that are out of the protocol-defined visit windows (see table below) will not be included in the immunogenicity summaries and tabulations per timepoint. However, they may be included in sensitivity analyses.

Table 2: Visit Windows for Immunogenicity Analysis – Cohort 1

Analysis time point label (Relative to Day 1)	Reference day	Target day (from reference day)	Window of target day (days)
Day 1	Day of vaccination 1	1	(-∞, 1]
Day 15	Day of vaccination 1	15	[13, 17]
Day 29	Day of vaccination 1	29	[26, 32]
Day 57	Day of vaccination 1	57	[54, 60]
Day 85	Day of vaccination 2 ^a	29	[26, 39]
Day 183	Day of vaccination 1	183	[169, 197]
Day 365	Day of vaccination 1	365	[305, 425]
Day 393	Day of vaccination 3 ^b	29	[26, 32]
Day 547	Day of vaccination 3 ^b	183	[169, 197]
Day 730	Day of vaccination 3 ^b	365	[335, 395]

Notes: ^a in case of missed vaccination 2, the actual date of missed vaccination 2 (i.e. the date of the day 57 visit) is used as a reference day.

^b in case of missed vaccination 3, the actual date of missed vaccination 3 (i.e. the date of the day 365 visit) is used as a reference day.

Table 3: Visit Windows for Immunogenicity Analysis – Cohort 2

Analysis time point label (Relative to Day 1)	Reference day	Target day (from reference day)	Window of target day (days)
Day 1	Day of vaccination 1	1	(-∞, 1]
Day 15	Day of vaccination 1	15	[13, 17]
Day 29	Day of vaccination 1	29	[26, 32]
Day 57	Day of vaccination 1	57	[54, 60]
Day 85	Day of vaccination 2 ^a	29	[26, 39]
Day 183	Day of vaccination 1	183	[169, 197]
Day 365	Day of vaccination 1	365	[335, 395]

Day 547	Day of vaccination 1	547	[517, 577]
Day 730	Day of vaccination 1	730	[700, 760]
Day 912	Day of vaccination 1	912	[882, 942]
Day 1095	Day of vaccination 1	1095	[1065, 1125]

Notes: ^a in case of missed vaccination 2, the actual date of missed vaccination 2 (i.e. the date of the day 57 visit) is used as a reference day.

Table 4: Visit Windows for Immunogenicity Analysis – Cohort 3

Analysis time point label (Relative to Day 1)	Reference day	Target day (from reference day)	Window of target day (days)
Day 1	Day of vaccination 1	1	(-∞, 1]
Day 15	Day of vaccination 1	15	[13, 17]
Day 29	Day of vaccination 1	29	[26, 32]
Day 57	Day of vaccination 1	57	[54, 60]
Day 85	Day of vaccination 1	85	[82, 95]
Day 183	Day of vaccination 1	183	[169, 197]
Day 365	Day of vaccination 1	365	[305, 425]
Day 393	Day of vaccination 2 ^a	29	[26, 32]
Day 547	Day of vaccination 2 ^a	183	[169, 197]
Day 730	Day of vaccination 1	730	[700, 760]
Day 744	Day of vaccination 3 ^b	15	[13, 17]
Day 758	Day of vaccination 3 ^b	29	[26, 32]
Day 912	Day of vaccination 3 ^b	183	[169, 197]
Day 1095	Day of vaccination 1	1095	[1065, 1125]

Notes: ^a in case of missed vaccination 2, the actual date of missed vaccination 2 (i.e. the date of the day 365 visit) is used as a reference day.

^b in case of missed vaccination 3, the actual date of missed vaccination 3 (i.e. the date of the day 730 visit) is used as a reference day.

2.2. Pooling Algorithm for Analysis Centers

Data from all study center will be pooled together.

2.3. Analysis Sets

Vaccine assignment will follow the as-treated principle.

The **Full Analysis (FA) Set** will include all participants who were randomized and received at least one dose of vaccine (active or placebo), regardless of the occurrence of protocol deviations or the type of vaccine (ie, Ad26.RSV.preF, RSV preF protein, Ad26.RSV.preF/RSV preF protein combination or mixture). All safety and participant information analyses will be based on the FA set.

The **Per-protocol RSV Immunogenicity (PPI) Set** will include all participants who were randomized and received the complete first dose and for whom immunogenicity data are available. Samples taken after a participant experienced a major protocol deviation expected to impact the immunogenicity outcomes will be excluded from the PPI analysis (based on the date/time of the deviation: DV.DVSTDC). The list of major protocol deviations expected to impact immunogenicity will be documented in the major protocol deviations criteria document that is finalized prior to database lock. These will also be indicated in the locked database.

In addition, the following samples will not be included in the PPI set:

- For participants who experience a natural RSV infection (based on RT-PCR, or other sources), samples collected after the natural infection will not be taken into account in the assessment of the immunogenicity of the selected regimen.
- If a subject misses one or more active dose(s) of the selected regimen but continues the planned visit schedule, samples after the missed active dose(s) will not be taken into account.

The analysis of all secondary and exploratory immunogenicity endpoints related to RSV will be based on the PPI set. Depending on the number of samples excluded, a post-hoc exploratory analysis might be performed, including the excluded samples. To visualize excluded samples, participant profiles from several assays might be repeated, indicating the excluded samples.

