Group	R	N	Day 1	Day 57
11	R2	24	Ad26.RSV.preF 1×10^{11} vp + Placebo*	Placebo
12	R2	42	Ad26.RSV.preF/ RSV preF protein mixture: 5×10^{10} vp/50 μ g + Placebo*	Placebo
13	R2	42	Ad26.RSV.preF/ RSV preF protein mixture: 1×10^{11} vp/50 μ g + Placebo*	Placebo
14	R2	42	Ad26.RSV.preF/ RSV preF protein mixture: 1×10^{11} vp/150 μ g + Placebo*	Placebo
15	R2	42	Ad26.RSV.preF/ RSV preF protein mixture: 5×10^{10} vp/150 μ g + Placebo*	Placebo
16	R2	36	Separate injections* : Ad26.RSV.preF 1×10^{11} vp + RSV preF protein 150 μ g	Placebo
17	R2	36	Ad26.RSV.preF/ RSV preF protein mixture: 1×10^{11} vp/150 μ g + Placebo*	Ad26.RSV.preF/ RSV preF protein mixture: 1×10^{11} vp/150 μ g
18	R2	24	Placebo + Placebo*	Placebo
R2 TOTAL:		288		

N: number of participants (*Note*: Data from Groups 9 and 10 of Cohort 1 will be pooled with those from Groups 16 and 17 of Cohort 2 up to Month 12); R: randomization; vp: viral particles

* Each injection to be given in opposite arms

Expanded Safety Cohort (Cohort 3)

In the expanded safety cohort, approximately 315 participants will be randomized in parallel to 1 of 3 groups (Groups 19 through 21; [Table 10](#) and [Table 11](#)). No pauses in enrollment for safety assessments are planned.

Participants will receive the selected one- or two-dose regimen from Cohort 2 or placebo.

If the one-dose regimen is selected (Groups 11 through 16 from Cohort 2), Groups 19 and 20 would receive the selected regimen on Day 1, and a booster at Month 12 (the selected regimen or placebo, respectively) and Month 24 (the selected regimen). Group 21 will receive placebo at all timepoints ([Table 10](#)).

If the two-dose regimen is selected (Group 17 of Cohort 2), Groups 19 and 20 would receive the selected regimen on Day 1 and Day 57, and a booster (the selected regimen or placebo, respectively) at Month 12. Group 21 will receive placebo at all three timepoints (Table 11).

Table 10: Study Design: Expanded Safety Cohort (Cohort 3) with One-dose Regimen and Month 12 and Month 24 Booster

Group	R	N	Day 1	Month 12	Month 24
19	R3	135	Selected Regimen	Selected Regimen	Selected Regimen
20	R3	135	Selected Regimen	Placebo for the Selected Regimen	Selected Regimen
21	R3	45	Placebo for the Selected Regimen	Placebo for the Selected Regimen	Placebo for the Selected Regimen
R3 TOTAL:		315			
OVERALL TOTAL:		667			

N: number of participants; R: randomization

Table 11: Study Design: Expanded Safety Cohort (Cohort 3) with Two-dose Regimen and Month 12 Booster

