11.1. Analysis Sets

Vaccine assignment will follow the as-treated principle.

The Full Analysis (FA) Set will include all participants who were randomized and received at least one dose of vaccine (active or placebo), regardless of the occurrence of protocol deviations or the type of vaccine (ie, Ad26.RSV.preF, RSV preF protein, Ad26.RSV.preF/RSV preF protein combination or mixture). All safety and participant information analyses will be based on the FA set.

The Per-protocol RSV Immunogenicity (PPI) Set will include all participants who were randomized and received the complete first dose, and for whom immunogenicity data are available, excluding participants with major protocol deviations expecting to impact the immunogenicity outcomes.

In addition, the following samples will not be included in the PPI set:

- For participants who experience a natural RSV infection (based on RT-PCR, or other sources), samples collected after the natural infection will not be taken into account in the assessment of the immunogenicity of the selected regimen.
- If a participant misses one or more active dose(s) of the selected regimen but continues the planned visit schedule, samples after the missed active dose(s) will not be taken into account.

The analysis of all secondary and exploratory immunogenicity endpoints related to RSV will be based on the PPI set. Depending on the number of samples excluded, a post-hoc exploratory analysis might be performed, including the excluded samples. To visualize excluded samples, participant profiles from several assays might be repeated, indicating the excluded samples.

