11.4. Immunogenicity Analyses

No formal hypothesis on immunogenicity will be tested. Descriptive statistics (geometric mean and 95% CI for ELISA and RSV neutralization assay; median and quartiles for IFN- γ ELISpot and ICS) will be calculated for continuous immunologic parameters at all timepoints. For the humoral assays, geometric mean fold rises from baseline and corresponding 95% CIs might additionally be calculated. Baseline is considered as the last available assessment before the first vaccination. Graphical representations of immunologic parameters will be made as applicable.

For categorical variables, frequency tables will be presented.

In addition, for the regimen selection cohort (Cohort 2), GMT ratios with corresponding 95% CI of the VNA A2 levels of the combination/mixture regimens on Day 29 for the one-dose regimens (Groups 12 through 16) and Day 85 for the two-dose regimen (Group 17) versus the Day 29 VNA A2 levels of the one-dose Ad26.RSV.preF regimen (Group 11) will be calculated. Therefore, a regression model will be fitted with the respective VNA A2 levels as dependent variable and the respective regimens and baseline levels as covariates, using Satterthwaite's method to calculate

the degrees of freedom and allowing different variances for the vaccines. The estimate and CIs obtained as such will be back-transformed (by exponentiation) to a GMT ratio and the corresponding CI. Note that the effect of additional factors, such as age and the interaction with the regimen, might also be explored in this model.

Note: Immunogenicity data from Groups 9 and 10 of the initial safety cohort (Cohort 1) will be combined with those from Groups 16 and 17 of the regimen selection cohort (Cohort 2).

The same model might be repeated for other assays.

In the expanded safety cohort (Cohort 3), the effect of the Month 12 and Month 24 booster will be assessed. Therefore, the following ratios for VNA A2 will be calculated:

- In the groups with an active vaccination at Month 12/Month 24, the ratio of the Month 12/Month 24 booster Day 29 level versus the prime Day 29 level with the corresponding 95% CI will be calculated.
- The groups with an active vaccination at Month 12/Month 24 will be compared to corresponding groups with placebo vaccination at Month 12/Month 24 by calculating the ratio with the corresponding 95% CI.

Note that the above might also be repeated for other assays.

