The primary analysis set for the above is the PPI set. As a sensitivity analysis, key tables may also be based on the FA set. Depending on their occurrence, the effect of natural infections might be further explored.

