informed consent will also be required for participants in Cohort 3 who will receive the Month 24 booster.

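### The per-protocol rule removes participants who miss the Month 12 injection from Group 19 but not from Group 20, which puts an avoidable, probably small, bias into the randomised booster contrast

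*SAP*

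**What the plan says.** Protocol 11.1 and SAP 2.3 carry the same sample-level exclusion from the PPI set. The SAP's condition is "If a subject misses one or more active dose(s) of the selected regimen but continues the planned visit schedule", and the consequence, in the protocol's words, is that "samples after the missed active dose(s) will not be taken into account". Neither document has a matching sentence for a missed placebo dose.

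For the one-dose option, Protocol 3.1.1 states: "Groups 19 and 20 would receive the selected regimen on Day 1, and a booster at Month 12 (the selected regimen or placebo, respectively". Group 20's Month 12 injection is therefore not an active dose, and the exclusion does not reach it.

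Protocol 11.4 plans the contrast that this affects: "The groups with an active vaccination at Month 12/Month 24 will be compared to corresponding groups with placebo vaccination at Month 12/Month 24", as a VNA A2 ratio with a 95% CI. On the analysis set it says "The primary analysis set for the above is the PPI set". The counterweight is optional: "As a sensitivity analysis, key tables may also be based on the FA set". SAP Section 6 names only the PPI set, and SAP 2.3 leaves a reanalysis with the excluded samples as a post-hoc possibility.

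SAP 2.1.2, Table 4, note a gives Cohort 3 a reference day for visit windows when the Month 12 vaccination is missed. The stated reason for SAP Amendment 4 ties these windows to the per-protocol analysis.

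**The concern.** Until the Month 12 injection, Groups 19 and 20 have had the same Day 1 regimen, and participants and sites are blinded. Missing that injection should therefore happen for the same reasons and at the same rate in both groups. Participants who miss it need not resemble the others: Protocol 10.2 lists related adverse events, worsening health, intercurrent illness and immunosuppressant use among the reasons for stopping vaccination.

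If these participants leave both groups, the groups remain comparable. If they leave one group only, the contrast picks up a difference between kinds of people as well as the effect of the booster. At stake is the only randomised comparison of boosted with unboosted participants after the same first dose. It serves a stated Cohort 3 objective, the need for a Month 12 booster.

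**Working it through.** **1. The plan's own precision figure.** Protocol 11.2.2 assumes an SD of 1 on the log2 scale and 5% dropout. It states a precision of about 0.53 log2 for Cohort 2. With Group 11 at 24 × 0.95 = 22.8 and a 42-participant group at 39.9, t × √(1/22.8 + 1/39.9) = 0.525. With whole participants (22 and 40) it is 0.531. The figure reproduces, so SD = 1 is used below.

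**2. Precision of Group 19 versus 20.** The documents state none. With 135 per group, 1.969 × √(2/135) = 0.240 log2, or ×0.85 to ×1.18 around the observed ratio.

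**3. Which samples the rule leaves in.**
- Group 19 participant who misses Month 12 and keeps attending: a missed active dose, so samples from Day 393 onward are out.
- Group 20 participant who does the same: a missed placebo dose, so the rule is silent and the samples stay in. Table 4, note a supports this reading. Samples after a missed active dose are already excluded, so in the PPI set a window after a missed dose matters essentially for placebo.

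**4. Formula.** Let m be the share who miss the Month 12 injection but are still sampled. Let d be the mean log2 VNA A2, without a booster, of those who take the injection minus that of those who miss it. Let β be the booster effect.
- Group 19 in the PPI set: μ_dosed + β
- Group 20 in the PPI set: (1 − m) μ_dosed + m μ_undosed
- Difference: β + m(μ_dosed − μ_undosed) = β + m × d

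The bias is m × d on the log2 scale, a factor of 2^(m × d) on the ratio.

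**5. Size.** The documents give neither m nor d, so every value here is an assumption.

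| m | d (log2) | m × d | Factor on ratio | Share of 0.24 half-width |
|---|---|---|---|---|
| 5% | 0.3 | 0.015 | 1.010 | 6% |
| 10% | 0.5 | 0.050 | 1.035 | 21% |
| 20% | 0.3 | 0.060 | 1.042 | 25% |
| 20% | 0.5 | 0.100 | 1.072 | 42% |

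A wider range (m 2–20%, d 0.25–1) gives ×1.003 to ×1.15.

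**6. Simulated check** (135 per group, true ratio 2.00, so β = 1; m = 10%, d = 0.5).
- Rule as written: 2.07, as 2^1.05 predicts.
- Same exclusion in both groups: 2.00.
- Everyone kept: 1.87, as 2^0.9 predicts. This is a valid randomised contrast, but of the effect of offering the booster rather than of receiving it.

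**7. Precision cost of a two-sided exclusion.** The SE now is √{1/[135(1 − m)] + [1 + m(1 − m)d²]/135}. After the change it is √{2/[135(1 − m)]}.
- m = 5%, d = 0.3: 0.1234 to 0.1249, up 1.2%.
- m = 20%, d = 0.5: 0.1302 to 0.1361, up 4.5%.

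A simulation with 128 per group gave 0.127 to 0.129 and 0.134 to 0.140, about 2–5%.

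**The case against.** **The samples kept in Group 20 are legitimate.** A missed saline injection does not change antigen exposure, so that participant still had the intended prime without a boost. This is a good reason to keep the samples when describing Group 20 alone. It does not make the two groups comparable, which is what the ratio needs. The two-sided rule also conditions on a post-randomisation event, but on one that cannot depend on the arm, because treatment and blinding are identical up to that injection.

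**The effect may be tiny.** Only people who miss the injection and still give in-window samples count; dropouts contribute nothing in either group. Protocol 10.3 allows a 10-day deferral and Appendix 1 allows 3 weeks for COVID-19 disruption, so misses may be few. The sign of d is assumed too. At the low setting (5%, 0.3) the fix hardly changes total error: √(0.1234² + 0.015²) = 0.124 now, against 0.125 after. At 20% and 0.5 it is 0.164 against 0.136. The endpoint is secondary in Cohort 3 and the analysis is descriptive, so no type I error rate is affected. All of this stands and limits the weight of the point.

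**The major-deviation list might already cover missed placebo doses.** It is a separate document. If it does cover them, the asymmetry disappears and SAP 2.3 need only say so.

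**Stronger readings that a reader might infer, but that the documents do not support:**
- That the contrast sets attenders against everyone. The excluded Group 19 participants do attend; that is a condition of the rule. Exclusions for infection, major deviations and out-of-window samples still apply to Group 20.
- That the same fault arises anew at Month 24. Groups 19 and 20 are then both due active vaccine, so new misses are treated alike. Only the Month 12 exclusions carry forward.
- That the Month 24 consent step makes it worse. Protocol 16.2.3 says that "informed consent will also be required for participants in Cohort 3 who will receive the Month 24 booster", but nothing says that someone who declines stays for later sampling.
- That comparisons with Group 21 need the same remedy. Group 21 never receives active vaccine, so its exposure history differs and symmetric exclusion would not restore comparability in the same way.
- That Cohort 2 needs it. The planned contrast sets Group 17 at Day 85 against Group 11 at Day 29, before Group 11's Day 57 placebo, so excluding Group 11 samples from Day 85 would not touch the comparator.

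**Conclusion.** The point holds for the Cohort 3 Group 19 versus Group 20 VNA A2 ratio from Day 393 onward in the PPI set. Day 29 data are unaffected. The rule as written compares dosed participants with dosed plus undosed ones, and a larger sample would not remove the bias.

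Under assumed values of 5–20% missing and 0.3–0.5 log2, the ratio is overstated by about 1–7%. At the top of that range the bias is 0.100/0.1302 = 0.77 standard errors, and 95% CI coverage falls to about 88%. If few injections are missed, the effect is negligible. The direction rests on dosed participants having the higher titres; the reverse would understate the ratio.

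The conclusion also rests on Group 20 samples being kept, which is inferred from the silence of the rule and the visit-window note. It is worth correcting because the correction is cheap and the existing safeguards are optional, not because the size is known to be large.

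**What to change.** 1. In SAP 2.3 and Protocol 11.1, add that for the Group 19 versus 20 comparison after Month 12, samples taken after a missed Month 12 injection, active or placebo, are excluded in both groups, and that this carries forward to later Group 19 versus 20 time points. The present rule can stay for single-group descriptive tables.
2. Report the number of missed Month 12 injections by group, with the number of those participants still sampled. This shows how large m was.
3. Make the Group 19 versus 20 ratio in the full analysis set a planned sensitivity analysis. State that it is by randomised group, because both documents otherwise assign vaccine as treated.
4. If the major-deviation list already covers missed placebo doses, say so in SAP 2.3 instead of item 1.

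The cost is a sentence in each document, a flag derivable from the dosing records and one additional table. A few Group 20 samples leave the per-protocol contrast, which raises its standard error by roughly 1–5% under the assumed shares.
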